5.3.2 Blinding

SD-IIV4, HD-IIV4, and/or placebo will be administered to blinded participants in the opposite deltoid muscle, to which the mRNA COVID-19 vaccine was administered at Visit 1. SD-IIV4 or HD-IIV4 will be administered by unblinded licensed staff. In order to keep the participant blinded, the vaccine administrator will keep the prefilled syringes out of view of the participant at all times and will instruct the participant to turn their head in the opposite direction of the arm in which the vaccine is being administered. Similar instructions will be given to any persons accompanying the patient in the room. After administration, used study syringes will be disposed of according to site-specific SOPs. A licensed provider (MD, DO, NP, PA, RN, LPN), who will be trained on treating adverse reactions, will be immediately available at the time of vaccine administration along with emergency management supplies available for initial treatment of an allergic reaction if needed. Additionally, clinical members of the blinded data collection team will be present to assist study subjects.

5.3.3 Unblinding

A copy of participant treatment assignments will be retained at the site in a REDCap database file accessible only to the unblinded site staff. In the event of an occurrence when knowledge of the treatment assignment will influence subject's care, the Principal Investigator may be provided with the treatment assignment. The Principal Investigator must contact the Lead Site, Duke and document the event with information regarding the reasons for unblinding. After discussion with the Lead site, the Principal Investigator may receive the treatment assignment from the Lead site or if necessary, from the on-site secure file by the unblinded staff. Unblinding events should be reported to the CDC.

All subjects will be unblinded at the end of study and informed of whether they received the influenza and COVID vaccines either sequentially or simultaneously.

5.3.4 Incorrect Dose Administration

In the event that a participant who is ≥ 65 years of age inadvertently receives standard-dose influenza vaccine rather than high-dose influenza vaccine, using shared decision making, they will be offered the opportunity to receive the preferred high-dose influenza vaccine a minimum of 28 days following the receipt of the standard-dose vaccine. Although there is no current recommendation to follow receipt of a standard-dose vaccine by a high-dose vaccine, participants will be offered high-dose vaccine to assure they achieve optimal protection from infection. A minimum interval of 28 days was chosen based on the routine practice of administering two separate standard-doses influenza vaccine 28 days apart in children who are influenza vaccine naïve. Participants choosing to receive a subsequent high-dose influenza vaccine will be called on Days 3 and 8 following receipt of their vaccine to review for the occurrence of any unsolicited adverse events. They will continue to be followed for the occurrence of AESIs and SAES as outlined in Section 5.4 below.

5.4 Reactogenicity and Safety Assessment

Participants will be assessed for any immediate reactogenicity in a period at least 30 minutes after vaccine administration while at the study site. They will be assessed for the following potential systemic reactions such as anaphylaxis related symptoms (e.g., dyspnea, chest tightness, wheezing, cough, stridor, urticarial, flushing, nasal congestion, dizziness, syncope, diaphoresis, emesis) or other medical symptoms (e.g., feverishness, chills/shivering, fatigue, myalgia, arthralgia, headache, nausea/vomiting, diarrhea). They will be assessed for any potential injection site reactions including pain, tenderness, erythema or induration.

Frequency and occurrence of solicited local and systemic reactogenicity will be assessed daily through post-vaccination Day 7 following Visits 1, 2 and 3 (if primary two-dose COVID-19 vaccine series) using a standard memory aid. Participants/participant's LAR(s) will submit this information electronically on a daily basis. For participants unable to submit electronically, paper memory aid completion and collection will be acceptable but not preferred. Injection site and systemic solicited events will be graded as noted in **Tables 8 and 9**⁴⁵. Participants/participant's LAR(s) will be further queried upon presence of symptoms. Unsolicited adverse events (AEs) will be assessed during the first 7 days following each vaccination visit and concomitant medications will be assessed from 30 days prior to Visit 1 through the study period. Serious AEs (SAEs) and new onset of adverse events special interest (AESI) will be assessed through the entire period of a subject's participation (see below). Unsolicited AEs and SAEs will also be graded as to whether they are noticeable but do not interfere with activity (Grade 1), interfere

with some activity but did not need a medical visit or absenteeism (Grade 2), or prevent daily activity and/or resulted in medical visit and/or absenteeism (grade 3) or require an emergency room visit or hospitalization (Grade 4).

At the time of study enrollment, participants/participant's LAR(s) will be given a thermometer and instructed on using the symptom diary to document oral temperatures and post-injection symptoms. Beginning on the evening of Study Visits 1, 2 and 3 (if primary two-dose COVID-19 vaccine series) (Day 1) following vaccination, participants/participant's LAR(s) will record their or their child's oral temperature using the study-supplied thermometer, the occurrence of solicited AEs, for the next 7 days (Day 1 – 7). Temperature will be recorded at roughly the same time each day. If a temperature $\geq 100.0^{\circ}\text{F}$ (37.8°C) is recorded, a second measurement will be taken. If more than one temperature is taken on the same day, the highest temperature should be recorded. Fever will be defined as a measured temperature $\geq 100.4^{\circ}\text{F}$ (38.0°C). Participants/participant's LAR(s) will be queried during Visits 2, 3, and 4 on any solicited adverse events following vaccination. Injection site reactogenicity will be assessed separately for COVID-19 vaccine and IIV4 or placebo as described in **Table 8**.

Table 8. Injection-site Reactogenicity Grading

Local Reaction to Injectable Product	Mild (Grade 1)	Moderate (Grade 2)	Severe (Grade 3)	Potentially Life Threatening (Grade 4)
Pain	Noticeable but does not interfere with activity	Interferes with activity but did not need a medical visit or absenteeism [i.e. missing work or school]	Significant; prevents daily activity and/or resulted in medical visit and/or absenteeism [i.e. missing work or school]	Requires an emergency room (ER) visit or hospitalization
Induration/Swelling (≥ 12 years of age)	2.5 – 5 cm	5.1 – 10 cm	> 10 cm	Requires an emergency room (ER) visit or hospitalization
Induration/Swelling (< 12 years of age)	0.5 – 2 cm	2.0 -7.0 cm	> 7 cm	Requires an emergency room (ER) visit or hospitalization
Erythema/Redness (≥ 12 years of age)	2.5 – 5 cm	5.1 – 10 cm	> 10 cm	Requires an emergency room (ER) visit or hospitalization
Erythema/Redness (< 12 years of age)	0.5 – 2 cm	2.0 -7.0 cm	> 7 cm	Requires an emergency room (ER) visit or hospitalization
Axillary (underarm) swelling or tenderness ipsilateral to side of injection	Noticeable but does not interfere with activity	Interferes with activity but did not need a medical visit or absenteeism [i.e. missing work or school]	Significant; prevents daily activity and/or resulted in medical visit and/or absenteeism [i.e. missing work or school]	Requires an emergency room (ER) visit or hospitalization

Table 8. Injection-site Reactogenicity Grading

Local Reaction to Injectable Product	Mild (Grade 1)	Moderate (Grade 2)	Severe (Grade 3)	Potentially Life Threatening (Grade 4)
			missing work or school]	

Participants/participant's LAR(s) will also be queried during Visits 2, 3, and 4 on common post-injection systemic symptoms as described in **Table 9**.

Table 9. Systemic Reactogenicity Grading (FDA modified)

Systemic	Mild (Grade 1)	Moderate (Grade 2)	Severe (Grade 3)	Potentially Life Threatening (Grade 4)
Fever (°C) (°F)	38.0 - 38.4 100.4 - 101.1	38.5 - 38.9 101.2 - 102.0	39.0 – 40.0 102.1-104.0	> 40.0 >104.0
Nausea/vomiting	Noticeable but does not interfere with activity or 1 – 2 episodes/24 hours	Some interference with activity or > 2 episodes/24 hours	Significant; prevents daily activity and/or resulted in medical visit and/or absenteeism [i.e. missing work or school]	Requires an ER visit or hospitalization
Diarrhea	Noticeable but does not interfere with activity or 2 – 3 loose stools/24 hours	Some interference with activity or 4-5 loose stools/24 hours	Significant; prevents daily activity and/or resulted in medical visit and/or absenteeism [i.e. missing work or school] or 6 or more watery stools or > 24 hours	Requires an ER visit or hospitalization
Headache	Noticeable but does not interfere with activity	Some interference with activity but did not need a medical visit or absenteeism [i.e. missing work or school]	Significant; prevents daily routine activity and/or resulted in medical visit and/or absenteeism [i.e. missing work or school]	Requires an ER visit or hospitalization
Fatigue	Noticeable but does not interfere with activity	Some interference with activity but did not need a medical visit or absenteeism [i.e. missing work or school]	Significant; prevents daily routine activity and/or resulted in medical visit and/or absenteeism [i.e. missing work or school]	Requires an ER visit or hospitalization
Myalgia	Noticeable but does not interfere with activity	Some interference with activity but did not need a medical visit or absenteeism [i.e. missing work or school]	Significant; prevents daily routine activity and/or resulted in medical visit and/or absenteeism [i.e. missing work or school]	Requires an ER visit or hospitalization
Arthralgia	Noticeable but does not interfere with activity	Some interference with activity but did not need a medical visit or absenteeism [i.e. missing work or school]	Significant; prevents daily routine activity and/or resulted in medical visit and/or absenteeism [i.e. missing work or school]	Requires an ER visit or hospitalization
Chills	Noticeable but does not interfere with activity	Some interference with activity but did not need a medical visit or absenteeism [i.e. missing work or school]	Significant; prevents daily routine activity and/or resulted in medical visit and/or absenteeism [i.e. missing work or school]	Requires an ER visit or hospitalization

During Visits 2, 3, 4 participants/participant's LAR(s) will be encouraged to report any significant adverse events occurring within 7 days of the vaccination visits and during Visits 2, 3, 4, 5, and 6 any serious adverse events in an open-ended question format, e.g. "How are you or your child doing? Are you or your child having any medical or clinical problems? If so, please tell me about them." Participants/participant's LAR(s) who report severe solicited or unsolicited adverse events or express any concern about symptoms/unsolicited events will be encouraged to follow up with their or their child's primary care provider. Study staff will assist with coordination of referral appointments as necessary. Medical records will be obtained and reviewed for the occurrence of any adverse events, serious adverse events or adverse events of special interest throughout the study period.

Unsolicited adverse events (AEs) will be collected and reported for the 7 days following each vaccine visit. Serious adverse events (SAEs) and adverse events of special interest (AESI) will be collected and reported during the entire study period [i.e. from enrollment through 120 days following enrollment]. Unsolicited AEs, SAEs, and AESIs will be graded as follows.

Mild (Grade 1)	Moderate (Grade 2)	Severe (Grade 3)	Potentially Life Threatening (Grade 4)
Noticeable but does not interfere with activity or measurement	Interferes with activity but did not need a medical visit or absenteeism [i.e. missing work or school]	Significant; prevents daily activity and/or resulted in medical visit and/or absenteeism [i.e. missing work or school]	Requires an ER visit or hospitalization

An adverse event (AE) is any untoward medical occurrence in a patient or clinical investigation subject administered a pharmaceutical product and which does not necessarily have to have a causal relationship with this treatment.

An SAE is defined as an AE that meets one of the following conditions:

- Results in death during the period of protocol-defined surveillance
- Is life-threatening (defined as immediate risk of death at the time of the event)
- Requires inpatient hospitalization or prolonged hospitalization during the period of protocol-defined surveillance
- Results in congenital anomaly or birth defect
- Results in a persistent or significant disability/incapacity
- Any other important medical event that may not result in death, be life threatening, or require hospitalization, may be considered an SAE when, based upon appropriate medical judgment, the event may jeopardize the participant and may require medical or surgical intervention to prevent one of the outcomes listed above. Examples of such medical events include allergic bronchospasm requiring intensive treatment in an emergency room or at home, blood dyscrasias or convulsions that do not result in inpatient hospitalization, or the development of drug dependency or drug abuse.

An adverse event of special interest (AESI) includes the following:

- COVID-19 illness
- Multisystem inflammatory syndrome
- Guillain-Barre syndrome

- Allergic type reactions (including anaphylaxis, hives, or facial and limb swelling occurring within 7 days of a vaccination visit)
- Myocarditis or pericarditis

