
2. To further characterize and describe the proportion of participants in the Simultaneous and Sequential groups with local or systemic reactogenicity events of greater severity following each vaccination visit and cumulatively
	
2a. The proportion of participants reporting at least one moderate or greater or at least one severe or greater solicited local or systemic reactogenicity event in each vaccination group within 1-7 days following the first vaccination during which participants receive either IIV4 or placebo with an mRNA COVID-19 vaccine
 
2b. The proportion of participants reporting at least one moderate or greater or at least one severe or greater solicited local or systemic reactogenicity event in each vaccination group within 1-7 days following the second vaccination visit which participants receive either IIV4 or placebo
 
2c. The proportion of participants reporting at least one moderate or greater or at least one severe or greater solicited local or systemic reactogenicity event in each vaccination group within 1-7 days following the third vaccination visit during which all participants receive an mRNA COVID-19 vaccine alone for those receiving two doses of mRNA COVID-19 vaccine
 
2d. The proportion of participants reporting at least one moderate or greater or at least one severe or greater solicited local or systemic reactogenicity event in each vaccination group within 1-7 days following all vaccination visits combined

3. To describe the proportion of participants in Simultaneous and Sequential groups experiencing at least one unsolicited adverse event and one adverse event of special interest and to characterize these events	
3a. The proportion of participants in each vaccination group with an unsolicited adverse event occurring during the 7 days post each vaccination visit according to severity and system organ classification
 
3b. The proportion of participants in each vaccination group with an adverse event of special interest occurring during the study period according to event type

4. To compare the change of health-related quality of life (HRQOL) from baseline in the Simultaneous versus Sequential groups following the Vaccination Visit 1	4a. Comparison between vaccination groups of the mean maximal change in score from baseline on the EuroQOL 5 dimensions-5 level (EQ-5D-5L) and EuroQOL visual analogue scale (EQ VAS) within 1-7 days following the first vaccination visit

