7.1.1 Sample Size

Safety: Four reactogenicity events were included in the primary statistical endpoint: fever, chills, myalgia, or arthralgia of moderate or greater severity. These were considered clinically meaningful and were solicited in both mRNA COVID-19 vaccine trials. Headache and fatigue were also solicited reactogenicity in both trials, but each occurred at the moderate-severe grade in >10% of participants after dose 1 placebo (in the Pfizer- Pfizer-BioNTech trial) and were thought to be less specific¹³. Based on data from prelicensure studies^{10,52,53}, we assume that 15% of participants will have at least one reaction of moderate severity or greater to include fever, chills, myalgia, or arthralgia reactogenicity event in the Sequential group. We have selected a clinically meaningful noninferiority margin of 10%. We plan to recruit a total of 450 participants and assume a 5% drop out rate, leaving N=428 or N=214 per study group. Statistical calculations show that with a one-side alpha level of 0.025, and 214 subjects in each group across all study sites, there is 82.6% power to be able to demonstrate that the proportion of participants with at least one severe solicited local or systemic reactogenicity event in the Simultaneous group is noninferior to the Sequential group. Enrollment in this study shall occur during two influenza season (2021-22, 2022-23).

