## 8.2 Secondary Objectives

1. SO1: To compare the proportion of participants with moderate or more severe fever, chills, myalgia, or arthralgia in the Simultaneous versus the Sequential Group following the first vaccination visit.

This proportion will be compared between the Simultaneous versus the Sequential Group using an exact Mantel-Haenszel statistic (calculated in Proc Logistic in SAS) in a stratified analysis by site to control for the randomization blocks at the two-sided alpha 0.05 level. The site adjusted odds ratio and corresponding 95% confidence interval for the proportion of participants with moderate or more severe fever, chills, myalgia, or arthralgia following the first vaccination visit will also be calculated.

2. SO2: To compare the proportion of participants with moderate or more severe fever, chills, myalgia, or arthralgia in the Simultaneous versus Sequential Group following the second vaccination visit.

These proportions will be compared between the Simultaneous versus the Sequential Group using an exact Mantel-Haenszel statistic (calculated in Proc Logistic in SAS) in a stratified analysis by site to control for the randomization blocks at the two-sided alpha 0.05 level. The site adjusted odds ratio and corresponding 95% confidence interval for the proportion of participants with moderate or more severe fever, chills, myalgia, or arthralgia following the second vaccination visit will also be calculated.

3. SO3: To describe the proportions of participants in the Simultaneous and Sequential vaccination groups with solicited local and systemic reactogenicity events according to severity grade after the first and second vaccination visit and third vaccination visit for those receiving two doses of mRNA COVID-19 vaccine.

Tables (one for each visit 1, 2, and 3) will be produced that summarize each solicited local and systemic reactogenicity event by classification (grades 1-4 as well as grades 2- 4 combined), for each vaccination group. These tables will have the number and percentage for each classification by vaccination group and the 95% confidence interval of the difference between the vaccination groups for the percentage of grades 3 and 4 combined.

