### 8.3 Exploratory Objectives

1. EO1: To compare the proportion of participants with moderate or more severe fever, chills, myalgia, or arthralgia in the Simultaneous versus Sequential Group following the third vaccination visit for those receiving two doses of mRNA COVID-19 vaccine.

This proportion will be compared between the Simultaneous versus the Sequential Group using an exact Mantel-Haenszel statistic (calculated in Proc Logistic in SAS) in a stratified analysis by site to control for the randomization blocks at the two-sided alpha 0.05 level. The site adjusted odds ratio and corresponding 95% confidence interval for the proportion of participants with moderate or more severe fever, chills, myalgia, or arthralgia following the first vaccination visit will also be calculated.

2. EO2: To further characterize and describe the proportion of participants in the Simultaneous and Sequential groups with local or systemic reactogenicity events of greater severity following each vaccination visit and cumulatively.

Tables for each visit 1, 2, and 3, as well as a combined visit table, will be produced that summarize the number of participants by vaccination group with at least one grade 1 or higher local or systemic reactogenicity event, as well as the number of participants by vaccination group with at least one grade 3 or higher local or systemic reactogenicity event. This table will have the number and percentage for each outcome by vaccination group and the 95% confidence interval of the difference between the vaccination groups will be presented.

3. EO3: To describe the proportion of participants in Simultaneous and Sequential groups experiencing at least one unsolicited adverse event and one adverse event of special interest and to characterize these events.

Tables will be produced that summarize participants experiencing at least one unsolicited adverse event and summarize participants experiencing at least one adverse event of special interest during the study period by vaccination group. These tables will have the number and percentage of participants experiencing either outcome by vaccination group and the 95% confidence interval of the difference between the vaccination groups. Listings with the clinical narratives will also be provided. The primary analysis population will be the Full Analysis Population 2.

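### The Grade 3 diarrhoea cell and the 2.0 cm cut for children under 12 do not give unique severity grades; the effect is confined to descriptive reactogenicity tables

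*Protocol*

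**What the plan says.** **Diarrhoea (Protocol Section 5.4, Table 9; SAP Section 8.2, Table 2).** The two tables are worded alike.

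- Grade 1: "Noticeable but does not interfere with activity or 2 – 3 loose stools/24 hours".
- Grade 2: "Some interference with activity or 4-5 loose stools/24 hours".
- Grade 3: a criterion on daily activity, medical visit or absenteeism, followed by "or 6 or more watery stools or > 24 hours".

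**Swelling and redness under 12 years (Protocol Section 5.4, Table 8; SAP Section 8.2, Table 1).** Grade 1 runs from 0.5 to 2 cm and Grade 2 from 2.0 to 7.0 cm. For participants aged 12 or over, Grade 1 stops at 5 cm and Grade 2 starts at 5.1 cm.

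**Where the grades are used.**

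- SAP Section 8.2, Secondary Objective 3 (SO3), tabulates every solicited event by grade and for Grades 2 to 4 combined. It gives the "95% confidence interval of the difference between the vaccination groups for the percentage of grades 3 and 4 combined".
- Protocol Section 2 defines Exploratory Objective 2 (EO2) as participants with "at least one moderate or greater or at least one severe or greater solicited local or systemic reactogenicity event". SAP Section 8.3 instead tabulates "at least one grade 1 or higher local or systemic reactogenicity event", together with Grade 3 or higher.
- SAP Section 8.3 re-analyses SO3 by baseline serostatus (EO5) and by vaccine product (EO6).

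**Where they are not used.** Protocol Section 7.1.1 states: "Four reactogenicity events were included in the primary statistical endpoint: fever, chills, myalgia, or arthralgia of moderate or greater severity".

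**The concern.** A grading scale should place each event in one grade. These tables fail to do so in two places.

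In the diarrhoea row, Grades 1 and 2 are defined by effect on activity or by stools per 24 hours. Grade 3 drops the time base from its count and adds a duration that is sufficient on its own. No other row of Table 9 grades by duration. A participant with two loose stools a day for two days, and no effect on activity, meets Grade 1 by the first column and Grade 3 by the third.

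In the rows for children under 12, a reading of exactly 2.0 cm belongs to two grades. The rows for age 12 and over separate cleanly, so exclusive cuts were evidently intended.

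Neither document says that the higher grade applies or gives any other tie-break. At stake is whether the published severe rate for diarrhoea, and the severe rate for any solicited event, mean what a reader would take them to mean. The moderate-or-greater rate for local reactions in young children would also depend on who coded it.

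**Working it through.** **1. Is the primary analysis affected?** Start from the plan's own figure. Protocol Section 7.1.1 gives a 15% rate in the Sequential group, a 10% margin, one-sided alpha of 0.025, and 450 participants less 5% (450 × 0.95 = 427.5, taken as 428, or 214 per group). With equal true rates and unpooled variance:

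- standard error = √(2 × 0.15 × 0.85 / 214) = 0.0345
- power = Φ(0.10 / 0.0345 − 1.96) = 0.826

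This reproduces the stated 82.6%. The endpoint is built from fever, chills, myalgia and arthralgia, and none of those rows contains either defect. The power is therefore unchanged by any correction. The same holds for Secondary Objectives 1 and 2 and Exploratory Objective 1, which use the same four events.

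**2. Which outcomes does each defect reach?**

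| Defect | Grades it can shift | SO3 | EO2 as SAP 8.3 is written | EO5, EO6 |
|---|---|---|---|---|
| Diarrhoea over 24 hours | 1 or 2 into 3 | by-grade rows; Grades 2–4 row; Grades 3–4 interval | Grade 3 or higher composite | inherited from SO3 |
| 2.0 cm under 12 years | between 1 and 2 | by-grade rows; Grades 2–4 row | none | inherited from SO3 |

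The 2.0 cm overlap enters no confidence interval in SO3 and no severe outcome.

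**3. How many participants could the duration clause move?** The documents do not give the share of diarrhoea lasting more than 24 hours, so it must be varied. Protocol Table 1 gives any diarrhoea after BNT162b2 Dose 1 as 11.1% (16–55 years) and 8.2% (over 55 years). Extra Grade 3 participants per group = 214 × rate × share:

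| Share over 24 hours (assumed) | Rate 11.1% | Rate 8.2% |
|---|---|---|
| 0% | 0 | 0 |
| 10% | 2.4 (1.1%) | 1.8 (0.8%) |
| 25% | 5.9 (2.8%) | 4.4 (2.1%) |
| 50% | 11.9 (5.6%) | 8.8 (4.1%) |
| 100% | 23.8 (11.1%) | 17.5 (8.2%) |

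These are upper figures for each share, because some of these participants may already be Grade 3 on another criterion. No comparable calculation is possible for the 2.0 cm overlap: the number of reactions recorded at that value is not given.

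**4. What does this do to a group difference?** Suppose duration alone adds Grade 3 diarrhoea with probability b in both groups, independently of other severe events. A composite rate p becomes p + (1 − p)b, and a difference d becomes (1 − b)d. With b between 0 and 0.111 (the 11.1% column), the difference shrinks by 0% to 11.1% of its value, and at a 25% share by 2.8%. Some variance is added as well.

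**The case against.** The strongest reply is that the literal reading may never have operated. The other count grades in the row are per 24 hours, so the last words may be a slip for a per-24-hour count. Protocol Section 5.4 describes daily assessment of frequency and occurrence and does not mention duration. The diary form is not in the documents. This stands as a reason not to claim that misgrading has occurred. It does not settle the point, because the final SAP repeats the wording and gives no derivation rule.

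A second reply is that both randomised groups are graded by the same table under observer blinding. That also stands: the rule does not by itself create a difference between groups. SO3 reports each event separately, so the diarrhoea row cannot contaminate severe fever or myalgia. Only the any-event composite is exposed.

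Three stronger readings are tempting but not supported.

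- A reader might infer that all diarrhoea becomes severe. Even read literally, only diarrhoea lasting more than 24 hours does.
- A reader might infer that the trial's severe and moderate-or-greater outcomes are wrong in general. The primary endpoint, Secondary Objectives 1 and 2 and Exploratory Objective 1 are moderate-or-greater comparisons, and none of them is touched.
- A reader might set the table above against the figure of at most 0.9% for severe systemic events in Protocol Section 1.1 (0.009 × 214 = 1.9 participants) and conclude that false severe events would swamp true ones. That figure is for BNT162b2 Dose 1 only. The same section gives Grade 3 systemic events for mRNA-1273 as 2.0% to 2.9% after Dose 1 (4.3 to 6.2 of 214) and 15.7% in the younger group after Dose 2 (33.6 of 214). It also describes booster reactogenicity as generally similar to Dose 2, and Section 1.2 expects most adults to be receiving boosters. The 0.9% is not a fair benchmark for this trial.

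**Conclusion.** The point holds as a minor inconsistency in the grading rules. Both defects appear in the protocol and the SAP alike, so a fault in reading the PDF is unlikely, and no tie-break resolves them. Some events in a secondary safety outcome therefore have no unique grade.

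The reach is limited to SO3 (chiefly the Grades 3–4 interval for diarrhoea and the Grades 2–4 rows), the Grade 3 or higher composite in EO2, and the SO3 re-analyses in EO5 and EO6. The size is unknown: 0 to about 24 extra Grade 3 participants of 214 per group, with about 2, 6 and 12 at shares of 10%, 25% and 50%. That range rests on an 11.1% diarrhoea rate borrowed from one vaccine and dose, on an assumed share, and on the clause being applied literally.

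The likely result is an inflated or noisy severity count. A reader might go further and infer that a real difference between groups would be hidden. The documents do not show this: under the independence assumption above, the dilution is at most 11.1% of the difference and is confined to the composite.

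**What to change.** 1. In Protocol Table 9 and SAP Table 2, reconcile the Grade 3 diarrhoea cell with its own row: put the six-stool count on a per-24-hour basis and remove duration as a stand-alone criterion (two cells).
2. In Protocol Table 8 and SAP Table 1, make the cuts for children under 12 mutually exclusive for swelling and for redness, for example by starting Grade 2 above 2.0 cm (four cells).
3. State in the SAP how an event that meets two grades is classified, and how the diary questions were worded and programmed.
4. Where stool counts and centimetre readings were recorded, derive the grades from them by program, so that diaries from both seasons are graded alike. If only the grade was recorded, say so beside the affected tables.
5. When SAP Section 8.3 is reconciled with the moderate-or-greater definition of EO2, apply the same cuts. The 2.0 cm overlap would otherwise reach that table too.

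The cost is six cell edits, a short SAP paragraph and one derivation. Sample size, visits and the primary analysis do not change.
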